A RANDOMIZED TRIAL OF THE SYNC APP

Protocol Number: UMCC 2020.157

National Clinical Trial (NCT) Identifier: NCT04827446

Principal Investigator: [name] [name], MS
[name]
[name]
[contact]
[contact]
Email: [contact]

Co-Investigators: [name] PhD, [name] MD PhD, [name]
MD, [name] PhD, [name] MD PhD

Biostatistician: [name] PhD
[contact]
Email: [contact]

Single Center: University of Michigan

Version: April 4, 2022

Table of Contents

PROTOCOL SYNOPSIS	3
STUDY SCHEMA: SCHEDULE OF EVENTS	6
TIME AND EVENTS TABLE	7
INTERVENTION ARM VS CONTROL ARM	8
1. BACKGROUND AND SIGNIFICANCE	9
2. STUDY DESIGN	13
3. STUDY ENDPOINTS	17
4. PATIENT ENROLLMENT AND EVALUATION	18
5. STATISTICAL CONSIDERATIONS	20
APPENDIX A: DESCRIPTION OF DEVICES	23
Fitbit Charge 3	30
Apple Watch	36
APPENDIX B: SYNC COMPONENTS	51
APPENDIX C: USER-REPORTED OUTCOME MEASURES	62
APPENDIX D: REFERENCES	60

PROTOCOL SYNOPSIS

A RANDOMIZED TRIAL OF THE SYNC APP

Principal Investigator: [name]

Study Design: This is a study to assess whether individually tailored lighting and behavioral interventions delivered through an app are able to reduce symptoms of fatigue and improve quality of life across three populations of cancer patients. We will recruit 138 patients (69 control, 69 interventional) across three cancer populations: breast cancer and prostate cancer, and patients who have undergone hematopoietic stem cell transplant (HSCT). Participants will be randomized 1:1 to either the interventional SYNC app or to a control app.

Primary Objective: The primary objective is to test the statistical significance or difference between the intervention arm and the control arm in the measured outcome of fatigue, as quantified by daily fatigue surveys and weekly PROMIS Short Form v. 1.0 Fatigue 4a surveys.

Secondary Objective: The secondary objective will be to assess user sleep disturbances, anxiety, depression, physical function, and global health via a suite of PROMIS questionnaires.

Exploratory Objectives: Exploratory objectives will be to assess: i) physical activity through physiological data capture using the wearable sensor; ii) health care utilization (i.e., total count of hospital days, ED visits, readmissions, and ambulatory care clinic visits), and iii) sleep aid usage, as measured by self-report.

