3. STUDY ENDPOINTS

3.1. *Primary Endpoint.* The primary endpoint is **fatigue**, as assessed by a daily fatigue questionnaire and a weekly 4-item PROMIS fatigue questionnaire.

3.2. *Secondary Endpoint.* The secondary endpoints are sleep disturbance, anxiety, depression, physical function and global health, as measured via the following PROMIS validated instruments:

- PROMIS Sleep Disturbance (8-item)
- PROMIS Anxiety (7-item)
- PROMIS Depression (8-item)
- PROMIS Physical Function (8-item)
- PROMIS Global Health (10-item)

3.3. *Exploratory Endpoints.*

3.3.1. Activity data. Patient activity (steps) and sleep will be measured continuously from the start to the end of the trial through wearable sensors.

3.3.2. Health care utilization data. Patient health care utilization data (e.g., total count of hospital days, emergency department visits, readmissions, and ambulatory care clinic visits) will be captured through the electronic health record as well as self-report (i.e., if the patient is readmitted at an outside hospital other than Michigan Medicine).

3.3.3. Sleep aid utilization data will be collected via self-report in the app once a week.

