- 5.6. *Primary Endpoint.* The primary objective of the study is to test the effects of SYNC in a randomized controlled clinical trial design. Patients will be randomly assigned to the treatment arm or the control arm. The primary objective is to quantify the effects of the light interventions delivered by SYNC on patient fatigue.
- 5.7. *Sample Size Considerations.* We will enroll 138 cancer patients, with half in the intervention arm and half in the control arm. Our primary endpoint is the PROMIS 4-item Fatigue Short Form. The age- and sex-adjusted norm for the Fatigue scale is 50 points, with a standard deviation of 10 points. These statistics have been shown to be largely generalizable to the cancer patient population (mean: 52, standard deviation 7.6). Our study will have power of 0.80, assuming a two-sided Type I error rate of 0.05, to detect an effect size of half the standard deviation between the intervention and control arms if 64 cancer patients are enrolled in each of the control and intervention groups. A mean difference of one-half a standard deviation is clinically meaningful and is considered a medium effect size for clinical trials. During the primary analysis, we will adjust for the fact

that there are three cancer populations in our data and will look for a well-defined effect that is marginal within each population. We will accrue a total of 69 patients in each arm to account for attrition of data, assuming a 7% dropout rate from the trial.

5.8. PROMIS® measures use Item Response Theory (IRT), a family of statistical models that link individual questions to a presumed underlying trait or concept of global health represented by all items in the scale. PROMIS® instruments are scored using item-level calibrations. The most accurate way to score a PROMIS® instrument is to use the Health Measures Scoring Service, which our Study Team has experience with. This method of scoring uses “response pattern scoring,” which uses responses to each item for each participant. Response pattern scoring is especially useful when there is missing data (i.e., a respondent skipped an item), or different groups of participants responded to different items).

There are four key features of the score for PROMIS® Fatigue:

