5.14.2. Patient health care utilization. The total count of hospital days, ED visits, readmissions, and ambulatory care clinic visits during the trial, with adjustment for follow-up, will be compared between arms using a Poisson regression model, with adjustment for potential mediating or moderating effects of patient characteristics, if needed. The data will be captured at the time of PRO assessments.

5.14.3. Patient sleep aid utilization. The total number of sleep aids being used by the patients, as well as the types, will be collected via weekly surveys over the course of the trial.

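### The plain Poisson model in Section 5.14.2 makes no provision for overdispersion, so its standard errors for hospital days will be too small; for the other utilization counts the size of the problem is unknown

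*Combined protocol and SAP*

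**What the plan says.** Section 3.3.2 defines the utilization endpoint as the "total count of hospital days, emergency department visits, readmissions, and ambulatory care clinic visits". Section 5.14.2 gives the whole analysis in one sentence. The method is that these counts, adjusted for length of follow-up, "will be compared between arms using a Poisson regression model". Covariates are left optional; the section allows the comparison to be made "with adjustment for potential mediating or moderating effects of patient characteristics, if needed".

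The combined document nowhere mentions overdispersion, a dispersion check, scaled or robust errors, or another count model. Sections 5.12 and 5.13, by contrast, do name a fallback for their t-tests (Wilcoxon, if normality fails). Section 5.14.2 does not say whether the four counts are summed or analysed one at a time, and it states no significance level.

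The Protocol Synopsis places utilization among the exploratory aims: "Exploratory objectives will be to assess: i) physical activity through physiological data capture using the wearable sensor; ii) health care utilization".

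**The concern.** A Poisson model fixes the variance equal to the mean and derives its standard error from that. Hospital days cannot satisfy this. Days arrive in runs, one run per admission, so a few patients contribute blocks of days and most contribute none. If the model is fitted as described, the confidence interval for the rate ratio is too narrow and the p-value too small.

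What is at stake is a false utilization signal. An excess of one or two long admissions in one arm, arising by chance, could be reported as an effect of the app on health care use. Adjusting for follow-up corrects for time at risk and does nothing about clustering of days within admissions.

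**Working it through.** **Inputs from the documents.** Enrolment is 69 per arm (Section 5.7). This reproduces: a two-sample t-test with a 0.5 SD difference and two-sided 0.05 has power 0.801 at 64 per arm, and 64 / (1 − 0.07) = 68.8, rounded up to 69. That calculation concerns fatigue. There is no stated rate, variance or power for utilization to reproduce. The 5% reference level is borrowed from Section 5.7 ("assuming a two-sided Type I error rate of 0.05").

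**Assumed inputs.** Admissions per patient over the trial 0.05 to 0.20; mean stay 3 to 8 days; two shapes for the stay distribution.

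**Step 1: effect of overdispersion on the test.** Let φ = variance / mean. The Poisson standard error is 1/√φ of the true one, and in large samples the actual two-sided type I error is 2 × [1 − Φ(1.96/√φ)].

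| φ | Reported SE / true SE | Actual type I error |
|---|---|---|
| 1.0 | 1.00 | 5.0% |
| 1.2 | 0.91 | 7.4% |
| 1.5 | 0.82 | 11.0% |
| 2 | 0.71 | 16.6% |
| 3 | 0.58 | 25.8% |
| 5 | 0.45 | 38.1% |
| 10 | 0.32 | 53.5% |

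Simulation of negative binomial counts (69 per arm, 40,000 replicates, mean 0.5 and mean 3) agrees: 11% at φ = 1.5, 16% at 2, 25–26% at 3, 37–38% at 5, 52–53% at 10.

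**Step 2: φ for hospital days.** If admissions are Poisson and stay length is L, then φ = E(L²)/E(L), which exceeds 1 whenever some stays last more than one day.
- Stays with little spread, L = 1 + Poisson(m − 1): φ = m + (m − 1)/m. For m = 3 this is 3.7; for m = 8 it is 8.9.
- Geometric stays with mean m: φ = 2m − 1. For m = 3 this is 5; for m = 8 it is 15.

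**Step 3: type I error for hospital days, simulated at 69 per arm with no effect.** The low-spread stays gave about 25% to just over 50%; geometric stays gave about 31% to 61%. Allowing at most one admission per patient changes little: 10% admitted with mean stay 5 gives φ = 5.3 and 39%; 15% admitted with mean stay 3 gives φ = 3.2 and 28%.

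**Step 4: one concrete case.** Suppose 22 days in one arm and 10 in the other. The log rate ratio is ln(2.2) = 0.788, the Poisson SE is √(1/22 + 1/10) = 0.381, z = 2.07 and p = 0.039. With φ = 5, z becomes 2.07/√5 = 0.92 and p is about 0.36. One or two long admissions can produce that 12-day gap.

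**Step 5: do differences between cancer populations contribute?** With assumed population means of 2, 3 and 8, Poisson counts within each population and 23 patients of each per arm (the balance intended in Section 5.4), the plain Poisson test rejected in 5.1% of trials. Balanced populations do not inflate the error.

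**Step 6: how well do the alternatives behave?** For negative binomial counts the dispersion-scaled (quasi-Poisson) test rejected 4.8–5.2% at mean 3 and 3.9–4.9% at mean 0.5. For simulated hospital days calibration is rougher: quasi-Poisson about 1–5%, sandwich errors about 2–11%, negative binomial Wald tests 0.1–5.7% and mostly under 3%. At 0.05 admissions per patient, the chance that at least one arm has no hospital days is 1 − (1 − e^(−69 × 0.05))² ≈ 6%, and then no finite rate ratio exists.

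**The case against.** The strongest reply is that the endpoint is exploratory, Section 5.14.2 sets no significance level, and a competent analyst would check dispersion in any case. The first two points stand and limit the severity. The third is not in the plan. Section 5.5 says the study team is not blinded, so choosing the count model after seeing the data is what pre-specification should prevent. Exploratory status also does not make a too-narrow interval right.

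Three stronger readings are tempting, and the documents do not support them.

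- A reader might infer that all four counts will show spurious significance. Only for hospital days does overdispersion follow from how the count arises. ED visits and readmissions over 12 weeks may be rare and close to Poisson, and the documents give no rates to settle it.
- A reader might blame the mix of HSCT, breast and prostate patients. With the balance that Section 5.4 intends, Step 5 shows no inflation. The plan also leaves room for cancer type as a covariate, though only optionally.
- A reader might expect that naming another model makes the intervals correct. Step 6 shows that none of the usual choices is well calibrated for sparse hospital days.

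**Conclusion.** The point holds. For hospital days, the analysis as written gives standard errors that are too small. Under the assumed admission rates and stays, type I error is about 25% to 60% against a nominal 5%; where it falls in that range depends largely on mean stay and on how variable stays are. For clinic visits, ED visits and readmissions the direction is the same if visits cluster within patients, but the size cannot be fixed from the documents: about 7%, 11%, 17% and 26% at variance/mean ratios of 1.2, 1.5, 2 and 3.

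Severity is minor. The sample size and the primary and secondary conclusions do not depend on this analysis.

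**What to change.** In Section 5.14.2, replace the plain Poisson model with the following:

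- Analyse each of the four counts separately, with a dispersion-adjusted model named in advance (quasi-Poisson, negative binomial, or Poisson with robust errors).
- Use log follow-up time as the offset and include cancer population as a covariate. The covariate matters once errors are dispersion-adjusted: in the Step 5 setting, with population left out, the quasi-Poisson and sandwich tests rejected in only 0.2% of trials.
- For hospital days and any other sparse count, take the p-value from a permutation test stratified by cancer population.
- Report the rate-ratio interval as approximate, and as not estimable if an arm has no events.

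The cost is a few sentences of SAP text and wider intervals. No new data, patients or procedures are needed. If a count turns out close to Poisson, the adjustment costs almost nothing: in simulation with φ = 1, the quasi-Poisson test rejected in 4.8% to 5.0% of trials.

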APPENDIX A: DESCRIPTION OF DEVICES

Participants in both arms will be given a pair of glasses. In the control group, participants will be given a pair of clear safety glasses. They will be given one of two types of clear glasses, depending on whether or not they wear reading glasses and comfort considerations.

The first type of glasses for the control group are those meant for participants who do not wear reading glasses. To account for changing availability of specific glasses models on the Amazon website, any pair of clear safety glasses that is similar to the model below may be used.

Example of control glasses for participants who do not wear reading glasses:

Crews BK310 BearKat 3 Polycarbonate Clear Lens Safety Glasses with Non-Slip Hybrid Black Temple Sleeve

Manufacturer	MCR Safety
Part Number	1
Item Weight	0.32 ounces
Package Dimensions	9 x 2.6 x 1.6 inches

Item model number	BK310
Color	Clear Lens
Style	Duramass Coated Lens
Finish	Scratch-resistant
Pattern	Safety Glasses
Item Package Quantity	1
Batteries Required?	No

The second type of glasses available to participants in the control group are larger and meant for participants who also wear reading glasses. To account for changing availability of specific glasses models on the Amazon website, any pair of clear safety glasses that is similar to the model below may be used.

Example of control glasses for participants who do wear reading glasses:

Safety glasses Industrial Goggles with Anti-fog Lens, Clear Safety glasses with Anti-Scratch Lens Goggles Inside Eyeglasses (Transparent)

Manufacturer	MEIGIX
Part Number	MEIGIX-GOGGLES2
Item Weight	2.82 ounces
Package Dimensions	9.09 x 4.53 x 2.8 inches
Finish	Scratch-resistant, Anti-fog, Uv-protection
Material	Plastic
Batteries Required?	No

Participants in the intervention arm will be given a pair of blue-blocking glasses. This will be one of two types depending on whether they wear reading glasses or not, as well as comfort considerations.

Participants in the intervention arm with reading glasses will receive blue-blocking glasses that fit over their other glasses. To account for changing availability of specific glasses models on the Amazon website, any pair of blue-blocking glasses that is similar to the model below may be used.

Example of intervention glasses for participants who do wear reading glasses:

Uvex ASTRO Over-The-Glass (OTG) Blue Light Blocking Computer Glasses with SCT-Orange Lens.

Manufacturer	Honeywell
Part Number	S2515
Item Weight	2.32 ounces
Package Dimensions	6.81 x 2.83 x 2.6 inches
Item model number	S2515
Style	ASTRO OTG
Item Package Quantity	1
Included Components	1 safety eyewear

Batteries Required?	No
---------------------	----

Participants in the intervention arm without reading glasses will receive smaller blue-blocking glasses that would not fit over other glasses. To account for changing availability of specific glasses models on the Amazon website, any pair of blue-blocking glasses that is similar to the model below may be used.

Example of intervention glasses for participants who do not wear reading glasses:

Uvex Skyper Blue Light Blocking Computer Glasses with SCT-Orange Lens.

Manufacturer	Uvex
Part Number	S1933X
Item Weight	1.6 ounces

Product Dimensions	2.7 x 2.2 x 7 inches
Item model number	S1933X
Is Discontinued By Manufacturer	No
Size	1-Pack
Color	Sct-orange Lens
Style	Skyper
Finish	Anti-fog
Item Package Quantity	1
Included Components	1 Pair of Glasses
Batteries Included?	No
Batteries Required?	No
Warranty Description	Lifetime Frame Guarantee

Participants in both arms will be given a wearable device. This device will be either a Fitbit Charge 3 or an Apple Watch.

In the event that Fitbit Charge 3s are the selected wearable device for the study, a description of the device follows below.

The Fitbit Charge 3 is a smart watch capable of measuring heart rate, exercise amount, and sleep levels. There is a retail version available, and that is the model we will be using for our study. The data collected by the Fitbit Charge 3 is transferred from the smart watch to the Fitbit application installed on the patient's phone via Bluetooth Low Energy (BLE), a form of Bluetooth specifically designed to lower power consumption without compromising range. The app then transmits the data to Fitbit's information management system securely and without identifiable information. The smart watch can be worn on either wrist to give accurate measurements. The Charge 3 is made of safe-to-use aluminum and flexible, non-elastic elastomer material common in fitness watches.

Participant Fitbits will be managed through Fitbit's proprietary management system. The user will grant the SYNC app permission to access their heart rate and steps data during the onboarding step. The subject will wear the Charge 3 as often as they like. This will begin the collection of the subject's data. The smart watch will upload the data to the patient's phone every 15 minutes via BLE. The data is then sent to the Fitbit, where it is housed in secure Microsoft Azure servers, compliant with ISO/IEC 27001:2006 industry standards of encryption.

In the event that the Apple Watch is the selected wearable device for the study, a description of the device follows below.

The Apple Watch is a smart watch capable of measuring heart rate, steps, and sleep levels. The retail version will be used in the study. The data from the Apple Watch is transferred via Bluetooth Low Energy to the participant's phone and stored in the Apple Health App. The smart watch can be worn on either wrist. The strap is made from liquid silicone rubber or nylon weave for wearing comfort.

Information collected by the watch can be accessed by the app after the user has granted permission via the Apple Health app.

The Apple Watch series used in this trial may range from Series 3 to Series 6 and may include Series SE.

Detailed descriptions of both the Fitbit Charge 3 and the Apple Watch use and care are below.

Fitbit Charge 3

Place Charge 3 around your wrist. If you need to attach a different size band, or if you purchased another band, see the instructions in "Change the band" on page 13.

Placement for all-day wear vs. exercise

When you're not exercising, wear Charge 3 a finger's width above your wrist bone.

For optimized heart-rate tracking while exercising:

During a workout, experiment with wearing your tracker a bit higher on your wrist for an improved fit. Many exercises, such as bike riding or weight lifting, cause you to bend your wrist frequently, which could interfere with the heart-rate signal if the tracker is lower on your wrist.

Wear your tracker on top of your wrist, and make sure the back of the device is in contact with your skin.

Consider tightening your band before a workout and loosening it when you're done. The band should be snug but not constricting (a tight band restricts blood flow, potentially affecting the heart-rate signal).

Handedness:

For greater accuracy, you must specify whether you wear Charge 3 on your dominant or non-dominant hand. Your dominant hand is the one you use for writing and eating. To start, the Wrist setting is set to non-dominant. If you wear Charge 3 on your dominant hand, change the Wrist setting in the Fitbit app:

From the Today tab in the Fitbit app, tap your profile picture > Charge 3 tile > Wrist > Dominant.

Change the band:

Charge 3 comes with a small band attached and an additional large, bottom band in the box. Both the top and bottom bands can be swapped with accessory bands, sold separately on fitbit.com. For band measurements, see "Band size" on page 48.

Remove a band:

1. Turn over Charge 3 and find the band latches.
2. To release the latch, press down on the flat button on the band.
3. Gently pull the band away from the tracker to release it.
4. Repeat on the other side.

Attach a new band:

To attach a new band, press it into the end of the tracker until you feel it snap into place.

If you have trouble attaching the band or if it feels loose, gently move the band back and forth to make sure it's attached to the tracker.

Notifications: Charge 3 can show call, text, calendar, and app notifications from your phone to keep you informed. Keep your tracker within 30 feet of your phone to receive notifications.

Set up notifications

Check that Bluetooth on your phone is on and that your phone can receive notifications (often under Settings > Notifications). Then set up notifications:

1. From the Today tab in the Fitbit app, tap your profile picture > Charge 3 tile.
2. Tap Notifications.
3. Follow the on-screen instructions to pair your tracker if you haven't already. Call, text, and calendar notifications are turned on automatically.
4. To turn on notifications from apps installed on your phone, including Fitbit and WhatsApp, tap App Notifications and turn on the notifications you want to see.

Note that if you have an iPhone or iPad, Charge 3 shows notifications from all calendars synced to the Calendar app. If you have an Android phone, Charge 3 shows calendar notifications from the calendar app you choose during setup.

See incoming notifications: A notification causes your tracker to vibrate. If you don't read the notification when it arrives, you can check it later by swiping down from the top of the screen.

Manage notifications: Charge 3 stores up to 10 notifications, after which the oldest are replaced as you receive new ones.

To manage notifications:

Swipe down from the top of the screen to see your notifications and tap any notification to expand it.

To delete a notification, tap to expand it, then swipe to the bottom and tap Clear.

To delete all notifications at once, swipe to the top of your notifications and tap Clear All.

Turn off notifications: Turn off certain notifications in the Fitbit app, or turn off all notifications in the quick settings on Charge 3. When you turn off all notifications, your tracker won't vibrate and the screen won't turn on when your phone receives a notification.

To turn off certain notifications:

1. From the Today tab in the Fitbit app on your phone, tap your profile picture > Charge 3 tile > Notifications.
2. Turn off the notifications you no longer want to receive on your tracker.
3. Sync your tracker to save your changes.

To turn off all notifications:

1. Press and hold the button on your tracker and swipe left to reach the quick settings screen (on Fitbit Pay-enabled trackers).
2. Tap DND to turn on do not disturb. The DND icon dims to indicate that all notifications, including goal celebrations and reminders to move, are turned off.

Note that if you use the do not disturb setting on your phone, you don't receive notifications on your tracker until you turn off this setting.

Answer or reject phone calls:

If paired to an iPhone or Android (8.0+) phone, Charge 3 lets you accept or reject incoming phone calls. If your phone is running an older version of the Android OS, you can reject, but not accept, calls on your tracker.

To accept a call, tap the check mark on your tracker's screen. Note that you can't speak into the tracker—accepting a phone call answers the call on your nearby

phone. To reject a call, tap the icon on your tracker's screen.

Respond to messages

If paired to an Android (8.0+) phone, Charge 3 lets you respond directly to text messages and notifications from certain apps on your tracker with preset quick replies.

To respond to a message:

1. Tap the notification on your tracker. To see recent messages, swipe down from the clock face.
2. Tap Reply. If you don't see an option to reply to the message, replies aren't available for the app that sent the notification.
3. Choose a text reply from the list of quick replies or tap the emoji icon to choose an emoji.

For more information, including how to customize quick replies, see help.fitbit.com.

Activity and Sleep:

Charge 3 continuously tracks a variety of stats whenever you wear it. Data automatically syncs when in range of the Fitbit app throughout the day.

See your stats:

Swipe up from the clock face on your tracker to see your daily stats, including:

Core stats	Steps taken today, distance covered, floors climbed, calories burned, and active minutes
-------------------	---

Hourly steps	Steps taken this hour, and the number of hours you met your hourly activity goal
Heart rate	Current heart rate and heart-rate zone, and resting heart rate
Exercise	Number of days you met your exercise goal this week
Cycle track	Information on the current stage of your menstrual cycle, if applicable
Sleep Duration and quality of your sleep	

Find your complete history and other information detected by your tracker, such as sleep data, in the Fitbit app.

Track a daily activity goal: Charge 3 tracks your progress toward a daily activity goal of your choice. When you reach your goal, your tracker vibrates and shows a celebration.

Choose a goal: Set a goal to help you get started on your health and fitness journey. To begin, your goal is to take 10,000 steps per day. Choose to change the number of steps, or pick a different activity goal depending on your device.

Track progress toward your goal on Charge 3. For more information, see "See your stats" on the previous page.

Track your hourly activity:

Charge 3 helps you stay active throughout the day by keeping track of when you're stationary and reminding you to move.

Reminders nudge you to walk at least 250 steps each hour. You feel a vibration and see a reminder on your screen at 10 minutes before the hour if you haven't walked 250 steps. When you meet the 250-step goal after receiving the reminder, you feel a second vibration and see a congratulatory message.

Track your sleep: Wear Charge 3 to bed to automatically track basic stats about your sleep, including your time asleep, sleep stages (time spent in REM, light sleep, and deep sleep), and

sleep score (the quality of your sleep). Charge 3 also tracks your estimated oxygen variation throughout the night to help you uncover potential breathing disturbances. To see your sleep stats, sync your tracker when you wake up and check the Fitbit app, or swipe up from the clock face on your tracker to check the Sleep tile in Fitbit Today.

Fitness and Exercise

Choose to automatically track exercise, or to track activity with the Exercise app and see real-time stats and a post-workout summary.

Sync Charge 3 with the Fitbit app and share your activity with friends and family, see how your overall fitness level compares to your peers, and more.

Track your exercise automatically

Charge 3 automatically recognizes and records many high-movement activities which are at least 15 minutes long. Sync your device to see basic stats about your activity in the Exercise tile in the Fitbit app.

For more information, including how to change the minimum duration before an activity is tracked, see help.fitbit.com.

Track and analyze exercise with the Exercise app

Track specific exercises with the Exercise app on Charge 3 to see real-time stats, including heart-rate data, calories burned, elapsed time, and a post-workout

summary on your wrist. For complete workout stats, and a workout intensity map if you used GPS, tap the Exercise tile in the Fitbit app.

Note: Charge 3 uses the GPS sensors on your nearby phone to capture GPS data.

Check your heart rate

Heart-rate zones help you target the training intensity of your choice. See your current zone and progress toward your maximum heart rate on your device next to your heart-rate reading. In the Fitbit app, you can see your time spent in zones during a particular day or exercise. Three zones based on American Heart Association recommendations are available, or you can create a custom zone if you have a specific heart rate you're targeting.

Default heart-rate zones:

Default heart-rate zones are calculated using your estimated maximum heart rate. Fitbit calculates your maximum heart rate with the common formula of 220 minus your age.

Icon Zone Calculation Description			
	Below Zones	Below 50% of your maximum heart rate	Below the fat burn zone, your heart beats at a slower pace. You're likely at rest or doing light activities such as taking a stroll.
	Fat Burn Zone	Between 50% and 69% of your maximum heart rate	In the fat burn zone, you're likely in a moderate activity such as a brisk walk. Your heart rate and breathing might be elevated, but you can still carry on a conversation.
	Cardio Zone	Between 70% and 84% of your maximum heart rate	In the cardio zone, you're likely doing a vigorous activity such as running or spinning.
	Peak Zone	Greater than 85% of your maximum heart rate	In the peak zone, you're likely doing a short, intense activity that improves performance and speed, such as sprinting or high-intensity interval training.

Custom heart-rate zones

Instead of using these 3 heart-rate zones, you can create a custom zone to target a specific heart-rate range in the Fitbit app.

Apple Watch

To use your Apple Watch Series 3 or later with watchOS 7, you need to pair your Apple Watch with an iPhone 6s or later with iOS 14 or later. Setup assistants on your iPhone and Apple Watch work together to help you pair and set up your Apple Watch.

WARNING: To avoid injury, read Important safety information for Apple Watch before using your Apple Watch.

Turn on, pair, and set up your Apple Watch

1. Put your Apple Watch on your wrist. Adjust the band or choose a band size so your Apple Watch fits closely but comfortably on your wrist.
For information about changing the band on your Apple Watch, see Remove, change, and fasten Apple Watch bands.
2. To turn on your Apple Watch, press and hold the side button until you see the Apple logo.
3. Bring your iPhone near your Apple Watch, wait for the Apple Watch pairing screen to appear on your iPhone, then tap Continue.
Or open the Apple Watch app on your iPhone, then tap Pair New Watch.

4. When prompted, position your iPhone so that your Apple Watch appears in the viewfinder in the Apple Watch app. This pairs the two devices.
5. Tap Set Up Apple Watch. Follow the instructions on your iPhone and Apple Watch to finish setup.

Tip: If you have difficulty seeing your Apple Watch or iPhone, VoiceOver or Zoom can help—even during setup. See Set up Apple Watch using VoiceOver or Use Zoom on Apple Watch. While it's pairing with your iPhone, your Apple Watch provides tips on how to interact with it. Tap Display, Digital Crown, and Side Button to learn more.

You can activate cellular service on your Apple Watch during setup. If you don't wish to, you can activate it later in the Apple Watch app on your iPhone. See Use Apple Watch with a cellular network.

Your iPhone and Apple Watch must use the same cellular carrier. However, if you set up an Apple Watch for someone in your Family Sharing group, you may use a cellular carrier different from the one used on the iPhone you manage it with.
Cellular service not available in all regions.

Trouble pairing?

- *If you see a watch face when you're trying to pair:* Your Apple Watch is already paired to an iPhone. You need to first erase all Apple Watch content and reset settings.
- *If the camera doesn't start the pairing process:* Tap Pair Apple Watch Manually at the bottom of the iPhone screen, and follow the onscreen instructions.
- *If Apple Watch isn't pairing with iPhone:* See the Apple Support article If your Apple Watch isn't connected or paired with your iPhone.

Unpair Apple Watch

1. Open the Apple Watch app on your iPhone.
2. Tap My Watch, then tap All Watches at the top of the screen.
3. Tap  next to the Apple Watch you want to unpair, then tap Unpair Apple Watch.

Pair more than one Apple Watch

You can pair another Apple Watch in the same way you paired your first one. Bring your iPhone near your Apple Watch, wait for the Apple Watch pairing screen to appear on your iPhone, then tap Pair. Or follow these steps:

1. Open the Apple Watch app on your iPhone.
2. Tap My Watch, then tap All Watches at the top of the screen.
3. Tap Pair New Watch, then follow the onscreen instructions.

See the Apple Support article [Use more than one Apple Watch with your iPhone](#).

To learn how to set up a watch for someone in your Family Sharing group, see [Set up Apple Watch for a family member](#).

Quickly switch to a different Apple Watch

Your iPhone detects the paired Apple Watch you're wearing and automatically connects to it.

[figure not shown]
Just put on a different Apple Watch and raise your wrist.

You can also choose an Apple Watch manually:

1. Open the Apple Watch app on your iPhone.
2. Tap My Watch, then tap All Watches at the top of the screen.
3. Turn off Auto Switch.

To see if your Apple Watch is connected to your iPhone, touch and hold the bottom of the watch

screen, swipe up to open Control Center, then look for the Connected status icon .

Pair Apple Watch to a new iPhone

If your Apple Watch is paired to your old iPhone and you now want to pair it with your new iPhone, follow these steps:

1. Use iCloud Backup to back up the iPhone currently paired to your Apple Watch (see the [iPhone User Guide](#) for more information).

2. Set up your new iPhone. On the Apps & Data screen, choose to restore from an iCloud backup, then select the latest backup.
3. Continue iPhone setup and, when prompted, choose to use your Apple Watch with your new iPhone.

When iPhone setup completes, your Apple Watch prompts you to pair it to the new iPhone. Tap OK on your Apple Watch, then enter its passcode.

For more information, see the Apple Support article [How to pair your Apple Watch with a new iPhone](#).

Transfer an existing cellular plan to a new Apple Watch

[figure not shown]
You can transfer your existing cellular plan from your Apple Watch with cellular to another Apple Watch with cellular by following these steps:

1. While wearing your Apple Watch, open the Apple Watch app on your iPhone.
2. Tap My Watch, tap Cellular, then tap  next to your cellular plan.
3. Tap Remove *[name of carrier]* Plan, then confirm your choice.
You may need to contact your carrier to remove this Apple Watch from your cellular plan.
4. Remove your old watch, put on your other Apple Watch with cellular, tap My Watch, then tap Cellular.

[figure not shown]
Follow the instructions to activate your watch for cellular.

For more information about setup and pairing, see the Apple Support article [Set up your Apple Watch](#).

[figure not shown]
If you need to charge your Apple Watch before setup, see [Charge Apple Watch](#).

[figure not shown]
Apple Watch SE

Apple Watch Series 4 and Apple Watch Series 5

Apple Watch Series 3

Charge Apple Watch

Set up the charger

1. In a well-ventilated area, place the included Apple Watch Magnetic Charging Cable or Apple Watch Magnetic Charging Dock on a flat surface.
2. Plug it into the power adapter (sold separately).
3. Plug the adapter into a power outlet.

Begin charging Apple Watch

[figure not shown]
Place the Apple Watch Magnetic Charging Cable on the back of your Apple Watch. The concave end of the charging cable magnetically snaps to the back of your Apple Watch and aligns it properly.

You hear a chime when charging begins (unless your Apple Watch is in silent mode) and see a charging symbol  on the watch face. The symbol is red when Apple Watch needs power and turns green when Apple Watch is charging.

[figure not shown]
You can charge your Apple Watch in a flat position with its band open, or on its side.

- *If you're using the Apple Watch Magnetic Charging Dock:* Lay your Apple Watch on the dock.
- *If your battery is very low:* You may see an image of the Apple Watch Magnetic Charging Cable and the low battery symbol  on the screen. For more information, see the Apple Support article [If your Apple Watch won't charge or it won't turn on](#).

[figure not shown]
Apple Watch Series 6
